7 ASSESSMENT AND FOLLOW-UP

7.1 Discharge Protocol

Patients from the all therapy arms will enter the Discharge protocol 12 weeks \pm 14days post-1st Intervention providing no ongoing symptoms are presented before this.

Patients will be given the centre's Research Nurse contact details and are able to request an unscheduled visit if they experience recurrent symptoms and need hospital review. A blinded research Nurse or designee will contact the patient by telephone every 3 months to ensure that no endpoints have occurred.

The patient will be advised that the blinded research Nurse or designee making the phone call will not know which treatment they have received and the patient will be given a copy of the questions that they will be asked.

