7.1.1 Patients unable to enter the Discharge Protocol

Patients not able to enter the discharge protocol at 12 weeks will have necessary advice (further OPD, procedure) which will be a primary endpoint. The date of the endpoint will be the date of the subsequent event. These patients will be followed up at their usual study visits at M6, M9 and Final visit.

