11.2 Data Analysis

Primary outcome: Failure is counted when a patient experiences any hospital episode related to treatment for atrial arrhythmia. Patients are censored from their treatment group when they switch to a treatment other than that to which they were originally assigned or when they leave their treatment group without having experienced a hospital episode.

Data will be analyzed using the intention-to-treat principle and a p value of 0.05 or less will be considered significant. Primary outcome will be analysed using Kaplan-Meier statistics and differences will be tested using log-rank test and proportional hazards models. Other outcomes will be compared using t-test for continuous and Chi-square test or Fisher exact test for categorical variables and the appropriate generalized linear model will be used.

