5.7. Randomisation

Eligible patients who have given written, informed consent and who meet all the inclusion criteria and no exclusion criteria will undergo 1:1:1 randomisation to an un-blinded treatment of either AVATAR-protocol AF Ablation, medical anti-arrhythmic therapy or conventional AF ablation. Randomisation will be performed electronically using the InForm electronic data capture system and will be stratified by site.

From the date of randomisation, the 1st Intervention date (ablation or anti-arrhythmic medication change) must occur 28 days \pm 7days after this, therefore an ablation procedure date will be identified according to local EP catheter lab availability for each consenting, eligible

patient and randomisation of the patient will then be scheduled for 28 days \pm 7 days from this available date.

The patient may be withdrawn from any AF ablation treatment by the Investigator if any safety concerns arise during the period between randomisation and the ablation which make the patient an unsuitable candidate for the procedure. The patient will then be withdrawn from the study.

6. Analysis Set

All treatment evaluation will be performed on the principle of intention to treat (ITT) with additional per-protocol analyses ran alongside if defined (see Section 8). The per-protocol analysis set will consist of patients who received treatment originally allocated.

A sensitivity analysis will also be performed excluding patients who are withdrawn from the study between randomisation and start of treatment / 1st intervention. Any subjects that have withdrawn during this period will still be required to attend the end-of-study follow-up visit.

7. Variables of Analysis

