7.1. Primary Endpoint Variable

Time from 1st intervention to any hospital episodes (Emergency Room or patient request for OPD) related to treatment for atrial arrhythmia that has been formally adjudicated by an independent committee as a primary endpoint. Failure to enter discharge protocol at the Week 12 Review will also result in the primary endpoint being met.

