8.2. Primary Endpoint Analysis

Failure is counted when a patient experiences any hospital episode related to treatment for atrial arrhythmia. Time to failure will be taken as the time from 1st Intervention to the time of event.

Data will be analysed using the intention-to-treat principle and a p-value of 0.025 or less will be considered significant. Primary outcome will be analysed using Kaplan-Meier statistics and differences between treatment arms will be assessed using log-rank testing and proportional hazards models. Models containing one or more of the following covariates may also be assessed if deemed necessary; site, weight, hypertension, number of anti-arrhythmic taken by patient prior to 1st intervention.

Primary endpoint analysis will be carried out between AVATAR-AF Ablation and the Anti-Arrhythmic drug treatment arm in order to investigate the primary objective. The secondary objective will be assessed by testing AVATAR-AF Ablation against the Conventional Ablation arm.

An additional per-protocol analysis will be carried out in conjunction with the above.

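### SAP 7.1 makes non-entry to the discharge protocol at week 12 a primary failure without stating a reason, so non-entry unrelated to arrhythmia can be scored as treatment failure

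*SAP*

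**What the plan says.** **SAP 7.1** defines the primary variable as time from 1st intervention to an arrhythmia-related hospital episode that an independent committee has adjudicated. It then adds a second route: "Failure to enter discharge protocol at the Week 12 Review will also result in the primary endpoint being met". For this route it states no reason for non-entry, no adjudication and no event date.

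**Protocol 7.1** lets patients in every arm enter the discharge protocol at 12 weeks "providing no ongoing symptoms are presented before this".

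**Protocol 7.1.1** covers those who cannot enter: "Patients not able to enter the discharge protocol at 12 weeks will have necessary advice (further OPD, procedure) which will be a primary endpoint". On timing it says "The date of the endpoint will be the date of the subsequent event", and on follow-up "These patients will be followed up at their usual study visits at M6, M9 and Final visit".

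**SAP 8.2** defines failure by episode only: "Failure is counted when a patient experiences any hospital episode related to treatment for atrial arrhythmia". It contains no censoring rule.

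**Protocol 11.2** does contain one. Among those censored are patients "when they leave their treatment group without having experienced a hospital episode". The same sentence also censors patients who switch treatment. That part is a different question and is left aside here.

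Death, with stroke, is a secondary endpoint (SAP 7.2). Neither document says how a death is handled in the primary analysis.

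**The concern.** SAP 7.1 has dropped the condition that makes Protocol 7.1.1 sensible, namely that the patient still needs hospital care for the arrhythmia. An event-free patient who is lost at week 6, dies of another cause at week 8 or misses the week 12 visit has not entered the discharge protocol. A programmer working from SAP 7.1 alone could code each of them as a primary event. So could a patient seen at week 12 but not entered for a reason unrelated to arrhythmia. SAP 8.2 and Protocol 11.2 would not count any of these as failures.

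If that coding were used, missing data would become efficacy events in the primary analysis. Balanced spurious failures pull the arms together and cost power. Unbalanced ones would also bias the comparison. Treatment is open-label, so this should not be left as a coding decision after the data are in.

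**Working it through.** **1. The plan's own figure.** Inputs from Protocol 11.1 and SAP 5.5: 12-month event proportions 0.63 (drugs), 0.40 (AVATAR) and 0.20 (conventional); 100 evaluable per arm; 103 events; two-sided alpha 0.025 (z = 2.241); Freedman log-rank; 7% loss; 107 randomised per arm.

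- Events: 100 × (0.63 + 0.40) = 103, as stated.
- HR = ln(1 − 0.40)/ln(1 − 0.63) = 0.514.
- Power = Φ(√events × (1 − HR)/(1 + HR) − z) = Φ(√103 × 0.486/1.514 − 2.241) = 0.846.
- AVATAR v conventional: HR = ln(0.80)/ln(0.60) = 0.437, 60 events, power 0.787.

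The plan states 0.80 for the first comparison. The formula gives somewhat more, so the stated figure is conservative and does not affect this point. The second agrees with the plan's claim of similar power.

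**2. Literal rule, closed form.** Let f be the share of otherwise event-free patients scored as failures for non-entry. The proportion p becomes p + f(1 − p). The documents give no value for f, so two are tried: 7% (all planned loss before week 12) and 1.75% (7% × 3/12, loss even over the year). Both are applied equally in all arms.

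| f | AVATAR v drugs: HR, power | AVATAR v conventional: HR, power |
|---|---|---|
| 0 | 0.514, 0.846 | 0.437, 0.787 |
| 1.75% | 0.522, 0.834 | 0.456, 0.762 |
| 7% | 0.547, 0.796 | 0.507, 0.689 |

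At f = 7% the added events per 107 patients are 107 × 0.07 × (1 − p): 4.5 AVATAR, 2.8 drugs and 6.0 conventional. The baseline here is a trial with no loss at all, so the table overstates what the rule itself costs.

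**3. Literal rule against censoring, by simulation.** The fairer comparison keeps the same lost patients and changes only how they are scored. Set-up: 107 per arm, exponential times matching the 12-month proportions, loss uniform over weeks 0 to 12, log-rank at two-sided 0.025, 3000 trials per scenario. Literal means an event at week 12. The alternative is censoring at loss.

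| Loss before week 12 | Comparison | Literal | Censored |
|---|---|---|---|
| 1.75% in both arms | 0.40 v 0.63 | 0.875 | 0.894 |
| 7% in both arms | 0.40 v 0.63 | 0.836 | 0.867 |
| 7% in both arms | 0.40 v 0.20 | 0.739 | 0.818 |
| 5% AVATAR only | 0.40 v 0.63 | 0.756 | 0.885 |
| 7% AVATAR only | 0.40 v 0.63 | 0.686 | 0.873 |

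Repeat runs agree within about 2 points. With no true effect (0.50 v 0.50) and 7% loss in AVATAR only, the rejection rate is 0.050 under the literal rule and 0.024 under censoring; 0.048 of the 0.050 goes against AVATAR.

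The first three rows use the plan's 7% with an assumption about timing. The last two also assume loss in one arm only, for which the documents give no basis. They show sensitivity, not expectation.

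**The case against.** The best defence is that the SAP wording presupposes a review. Failing to enter at the Week 12 Review reads naturally as the outcome of an attended assessment. Protocol 6.5 describes that assessment, and Protocol 7.1 makes ongoing symptoms the only bar to entry. Protocol 7.1.1 keeps non-entrants in follow-up, which cannot describe the dead or the lost. Protocol 8.4 sends suspected events to an adjudication committee and asks for a letter for each attendance. On that reading Protocol 11.2 censors leavers, and nobody is miscounted.

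This is a fair account of the likely intent, and it rules out a stronger claim that a reader might infer: that every lost, withdrawn, dead or absent patient is counted as a failure. No sentence in either document says so. But the SAP does not state the narrower meaning. Its non-entry route stands beside the adjudicated one, joined by the word also, and SAP 8.2 has no censoring rule to correct it. The reading that the attended-review wording rescues also leaves one gap: a patient who attends and is not entered for a non-arrhythmia reason.

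A reader might also infer that the spurious failures would fall mostly in the ablation arms, because SAP 5.7 has a withdrawal route for patients found unsuitable before ablation, and SAP 6 says of such withdrawals: "Any subjects that have withdrawn during this period will still be required to attend the end-of-study follow-up visit". The documents do not support this. Those patients have no 1st intervention and so no time zero, no week 12 and no event time for this endpoint. SAP 6 plans a sensitivity analysis that excludes them. How the main intention-to-treat analysis treats them is a separate gap. No figure for loss by arm is given.

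**Conclusion.** The point holds as a defect in a stated rule. SAP 7.1 is broader than Protocol 7.1.1, conflicts with the failure definition in SAP 8.2, and has no censoring rule behind it in the SAP. Applied literally, it can count non-arrhythmia non-entry as primary failure.

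The likely size is small. For AVATAR v drugs it is about 0 to 2 power points if the 7% loss is even over the year and balanced. It is about 3 to 4 points if all of it falls before week 12 in both arms, and power then still exceeds the planned 0.80 in the simulation. For AVATAR v conventional that second case costs about 8 to 9 points. These figures assume exponential event times and the plan's own proportions.

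Larger losses arise only if early loss is one-sided. If it fell on AVATAR alone, the error would run against AVATAR and would not create a false claim over drugs. Severity: moderate, not must-fix.

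**What to change.** **SAP 7.1.** Replace the last sentence with wording to this effect: a patient who is assessed at the Week 12 Review and is not entered into the discharge protocol because of atrial arrhythmia needing further outpatient review or a procedure meets the primary endpoint, as set out in Protocol 7.1.1 and subject to adjudication.

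**SAP 8.2.** Add that patients who die, withdraw, are lost or miss the Week 12 Review are not failures for that reason. They stay at risk on later contacts where there are any, and are otherwise censored at last contact.

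**Reporting.** Tabulate reasons for non-entry by arm, so that a reader can see whether early loss was balanced.

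The cost is two short text changes and a reason-for-non-entry flag. The downside is a few more censored patients. Patients withdrawn before 1st intervention need their own rule, because this rewording does not give them a time zero.

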7.2. Secondary Endpoint Variables

1. Time from 1st intervention to death or stroke from any cause.
2. Number of and time from 1st intervention to any of the following complications caused by:
 - Pericardial Effusion
 - Vascular Bleeding (>2 units)
 - Phrenic Nerve Palsy
 - PV Stenosis
 - Drug side-effects (including GI disturbance, skin irritation and other)
 - Other

3. Number of and time from 1st intervention to any hospital episodes which result in a change in therapy for atrial arrhythmia.

Information about trial adverse events will be collected from randomisation until the end of the trial.

7.3. Safety and Efficacy Variables

The following information will be recorded and reported to demonstrate treatment safety and efficacy:

- Vital Signs (variables including; weight, blood pressure, pulse, body temp)
- Physical Examination
- Patient Health Questionnaires
 - Quality of Life (QoL)
 - Atrial Fibrillation Effect on QualiTy-of-life (AFEQT)
 - Telephone Follow-up
- CHADSVASC score
- ECG (variables including; ventricular rate, PR & QRS interval)
- Concomitant Medications
- Pulmonary Vein Isolation Measurements of Ablation Treatments (variables including; total duration of freeze, number of applications, Grade 4 occlusions, lowest temperature)
- Protocol Deviations and Violations
- Adverse and Serious Adverse Events

7.4. Baseline and Demographic Variables

The following additional information will be recorded and reported:

- Baseline Demographics (variables including; age, gender, ethnicity, height, weight).
- Medical History (including past cardiovascular medication)
- Echocardiogram Results

8. Statistical Methodology

8.1. Baseline Demographics

Baseline demographic variables and other relevant clinical baseline characteristics (including, but not limited to, medical history, pulse rate, blood pressure, QoL/AFEQT questionnaire results, CHADSVASC score, echo-cardiology readings, ECG and 24hr holter monitor results) will be summarised for each treatment group.

Summaries of continuous variables will be presented as means and standard deviations if normally distributed, and as medians and inter-quartile ranges for skewed data, whilst categorical variables will be presented as frequencies and percentages.

8.2. Primary Endpoint Analysis

Failure is counted when a patient experiences any hospital episode related to treatment for atrial arrhythmia. Time to failure will be taken as the time from 1st Intervention to the time of event.

Data will be analysed using the intention-to-treat principle and a p-value of 0.025 or less will be considered significant. Primary outcome will be analysed using Kaplan-Meier statistics and differences between treatment arms will be assessed using log-rank testing and proportional hazards models. Models containing one or more of the following covariates may also be assessed if deemed necessary; site, weight, hypertension, number of anti-arrhythmic taken by patient prior to 1st intervention.

Primary endpoint analysis will be carried out between AVATAR-AF Ablation and the Anti-Arrhythmic drug treatment arm in order to investigate the primary objective. The secondary objective will be assessed by testing AVATAR-AF Ablation against the Conventional Ablation arm.

An additional per-protocol analysis will be carried out in conjunction with the above.

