MAIN EXCLUSION CRITERIA	
1. Contraindication to catheter ablation2. No carer to enable daycare discharge3. Arrhythmias other than AF documented unless they have had curative ablation (eg. for atrial flutter)§ – Please see page 13 for more details.4. No documentation of sinus rhythm within 3 months5. Valvular or other heart disease needing regular follow up6. EF <45% or moderate/severe LV dysfunction (determined by Echocardiogram in the last 6mths)7. Active gastrointestinal disease precluding anticoagulation or trans-oesophageal echocardiogram8. Renal failure with creatinine >200 µmol/L or on dialysis9. Active fever or infection10. Life expectancy shorter than the trial11. Allergy to contrast12. Severe cerebrovascular disease precluding daycare discharge13. Bleeding or clotting disorders or inability to receive heparin14. Uncontrolled diabetes (HbA1c ≥73 mmol/mol or HbA1c ≤64 mmol/mol and Fasting Blood Glucose ≥9.2 mmol/L (shown in the last six months without evidence of being brought under control)15. Serum Potassium [K⁺] <3.5 mmol/L or >5.0 mmol/L (shown in the last six months without evidence of being brought under control)16. Malignancy needing surgery, chemotherapy or radiotherapy17. Pregnancy or women of child-bearing potential not using a highly effective method of contraception18. Must not have previous (4 weeks prior to screening) or current participation in another clinical trial with an investigational drug or investigational device19. Unable to give informed consent

	20. Uncontrolled thyroid disease defined as abnormal thyroid function tests causing cardiac manifestations within the last 6mths 21. Unable to attend follow-up visits
NUMBER OF PATIENTS	321 patients, 1:1:1 randomisation
DURATION OF STUDY	1 year recruitment period/1 year follow-up for each patient
NUMBER OF SITES	13 United Kingdom sites
PRIMARY ENDPOINT	Time to any hospital episodes (Emergency Room or outpatient) related to treatment for atrial arrhythmia
SECONDARY ENDPOINTS	
 1. Time to Death or Stroke from any cause 2. Any complications caused by the procedure (pericardial effusion, bleeding >2 units, phrenic nerve palsy and other) or the anti-arrhythmic drug (GI disturbance, skin irritation and other) 3. All hospital episodes which result in a change in therapy for atrial arrhythmia

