6.2 Anti-arrhythmic therapy

The anti-arrhythmic agent or the change in dose that was discussed with the patient selected as the next line of treatment at the initial screening visit is initiated at the 1st Intervention date. The anti-arrhythmic treatment is chosen should be done in accordance with local practice and guidelines.

The patient will undergo 2 reviews prior to entering the Discharge protocol.

- ***Review 1 (4 weeks post-1st Intervention)***
- ***Review 2 (8 weeks post-1st Intervention)***

At each review, the patient can be left unchanged, have an increase in drug dose or change of agent as required. Review 1 at 4 weeks post 1st intervention can take place as a telephone follow up followed by a clinic visit if required. Following the 2 reviews, the patient enters the Discharge protocol at 12 weeks ± 14days.

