8.4 Endpoint Adjudication

The endpoint adjudication will be done by an independent Endpoint Adjudication Committee (EAC). The EAC will centrally review and classify suspected outcome events, verifying whether they meet protocol definitions. Any hospital episodes (Emergency Room or outpatient) related to treatment for atrial arrhythmia, Stroke or Death from any cause, Any complications caused by the procedure (pericardial effusion, bleeding >2 units, phrenic nerve palsy and other) or the anti-arrhythmic drug (GI disturbance, skin irritation and other), All hospital episodes which result in a change in therapy for atrial arrhythmia.

Any attendance to hospital or specialist cardiac clinic will require the documentation of a discharge letter or clinic letter for primary endpoint adjudication.

Definitions of study endpoints: see Appendix 2

9 Patient visit schedule

PROCEDURE	VISIT (Month)					
	SCREENING (M-0.5 \pm 14d)	1 ST INTERVENTION (M0 \pm 7d)	WK4 REVIEW (M1 \pm 7d)	WK8 REVIEW (M2 \pm 7d)	WK12 REVIEW (M3 \pm 14d)	EOS (M12 \pm 14d)
Obtain Informed Consent	X					
Eligibility Criteria	X					
Vital Signs	X				X	X
Physical Examination	X				X	X
Medical History Assessment	X				X	X
Concomitant Medications	X				X	X
Fasting Blood Sample	X					
Quality of Life Questionnaire	X					X
Allocate 1 ST Intervention date	X					
Randomisation *	X					
Initiate 1 ST Intervention		X				
Allocate possible ablation 're-do' date ** [†]		X				
Review anti-arrhythmic medication			X	X		
Post-ablation symptoms review ** [†]				X	X	
Enter Discharge Protocol					X	
Electrocardiogram						X
24-Hour Holter monitor tape						X
Echocardiogram	X					
Adverse Events		X	X	X	X	X
Study Endpoints			X	X	X	X
AFEQT patient questionnaire	X					X

* = Randomisation date to be scheduled 28d \pm 7d from allocation of 1ST Intervention date

** = AVATAR-protocol ablation arm patients only

† = Anti-arrhythmic therapy arm patients only

^ = Conventional ablation arm patients

10 Safety Reporting

Information about trial adverse events will be collected from randomisation until the end of the trial

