3.2. Secondary Objectives

To determine if antral AF ablation without electrophysiological confirmation of PV isolation performed as a daycare is less effective than the conventional approach.

4. Study Endpoints

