5.5. Sample Size

In this time-to-event study of hospital episodes, required sample numbers have been estimated using the log-rank test under the Freedman method based on the occurrence of first event during the 12-month follow-up period. The null hypothesis is that there is no difference in the distributions. Adopting a conservative approach, an initial two-sided alpha of 0.05 is chosen, given the need to allow for the inherent multiple testing between the three arms of the study, the conservative Bonferroni correction is applied and the alpha value used in the power calculations is reduced to 0.025.

Estimating the proportion experiencing a hospital episode in the follow-up period in the anti-arrhythmic arm as 0.63 and the corresponding proportion in the AVATAR ablation arm as 0.40, assuming the occurrence of 103 events, with 100 evaluable patients in each of the two treatment arms yields a power of 0.80. A similar power is obtained for the comparison of the AVATAR ablation arm (0.40) and the conventional AF ablation arm (0.20).

A sensitivity analysis indicates that these sample size estimates are reasonable. It is anticipated that the loss to follow-up will be small, approximately 7%. Consequently, 321 patients will be randomised in a 1:1:1 manner to a treatment strategy of either AVATAR protocol ablation, anti-arrhythmic therapy or conventional AF ablation and followed-up for 1 year.

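### Randomisation is stratified by site, but the primary log-rank and Cox analyses leave site out: the test is valid and not underpowered, but conservative if sites differ, and a pre-specified site-stratified analysis is a cheap improvement

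*SAP*

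**What the plan says.** Protocol 5.4 and SAP 5.7 describe allocation in the same words: "Randomisation will be performed electronically using the InForm electronic data capture system and will be stratified by site". No other stratification factor is named. The Protocol Summary gives "13 United Kingdom sites".

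For the analysis, Protocol 11.2 states: "Primary outcome will be analysed using Kaplan-Meier statistics and differences will be tested using log-rank test and proportional hazards models". SAP 8.2 names the same methods. Neither mentions strata. SAP 8.2 then adds: "Models containing one or more of the following covariates may also be assessed if deemed necessary; site, weight, hypertension". The fourth covariate on that list is the number of anti-arrhythmics taken before first intervention. No trigger or model form is given for these extra models.

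SAP 8.2 applies this plan to AVATAR against drugs (primary objective) and to AVATAR against conventional ablation. For the latter, SAP 3.2 asks whether the streamlined procedure "performed as a daycare is less effective than the conventional approach".

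The shells agree with the text. Table 4.2 lists observed and expected events by arm with a one-degree-of-freedom chi-square, and Table 4.3 has Treatment as its only model term. A stratified log-rank test would also have one degree of freedom, so the shells corroborate the point; Protocol 11.2 and SAP 8.2 carry it.

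The documents give no site sizes, block size or between-site variation in event rates.

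**The concern.** Stratifying the randomisation balances the arms within each site. If event rates differ between sites, that balance makes the true variance of the arm difference smaller than the variance an unstratified log-rank test assumes. The test then rejects too rarely under the null and gives up some power. Stratifying the analysis by site recovers it. If sites do not differ, stratifying costs a little power instead.

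Site differences are plausible but not established. Drug choice is local: "The anti-arrhythmic treatment is chosen should be done in accordance with local practice and guidelines". The endpoint is itself a care episode, and under SAP 7.1 failure to enter the discharge protocol at week 12 also counts, which depends partly on local clinical decisions. In the other direction, all arms follow one visit schedule (Protocol 6) and events are adjudicated centrally: "The EAC will centrally review and classify suspected outcome events, verifying whether they meet protocol definitions".

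What is at stake is efficiency, and a plan in which the analysis follows the randomisation. The validity of the result is not at stake.

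**Working it through.** **Inputs from the documents.** The 12-month event proportions are 0.63 (drugs), 0.40 (AVATAR) and 0.20 (conventional), with 100 evaluable per arm and 103 events for the first comparison (SAP 5.5: "Estimating the proportion experiencing a hospital episode in the follow-up period in the anti-arrhythmic arm as 0.63", and what follows it). Alpha is two-sided 0.025 per comparison (SAP 5.5 and 8.2). There are 13 sites.

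**Assumptions.** The between-site SD of the log hazard (0 to 0.8), the accrual pattern by site and the block size are not in the documents.

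**Step 1: the plan's own power figure (Freedman).** Power = Φ(√D × (1 − HR)/(1 + HR) − z), with z = 2.241 for two-sided 0.025.
- AVATAR against drugs: HR = ln(0.60)/ln(0.37) = 0.514; D = 100 × (0.63 + 0.40) = 103. Power = Φ(10.149 × 0.321 − 2.241) = 0.846. The 103 events reproduce. The stated power of 0.80 does not, but the difference is in the trial's favour.
- AVATAR against conventional: HR = ln(0.80)/ln(0.60) = 0.437; D = 100 × (0.40 + 0.20) = 60. Power = Φ(7.746 × 0.392 − 2.241) = 0.787, in line with the SAP's statement that power is similar.

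**Step 2: unstratified against site-stratified log-rank, by simulation.** There were 20,000 replicates per setting; nine sites with 8 and four with 7 patients per arm; exponential times, censoring at 12 months and no dropout. The site effect on the log hazard was normal, and each arm's hazard was solved so that the whole-arm 12-month rate stays at the SAP value. Monte Carlo SE of each change is 0.11 to 0.17 points; changes were taken before rounding.

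| Site SD | Drug-arm rate, 10th to 90th percentile site | 0.63 v 0.40: unstratified, stratified (change, points) | 0.40 v 0.20: unstratified, stratified (change, points) |
|---|---|---|---|
| 0 | 63% throughout | 0.870, 0.860 (−1.0) | 0.817, 0.811 (−0.6) |
| 0.3 | 49% to 77% | 0.875, 0.879 (+0.4) | 0.817, 0.819 (+0.2) |
| 0.5 | 41% to 85% | 0.888, 0.910 (+2.2) | 0.826, 0.841 (+1.5) |
| 0.8 | 31% to 94% | 0.906, 0.957 (+5.0) | 0.834, 0.883 (+4.9) |

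**Step 3: null rejection, nominal 2.5%, at SD 0, 0.3, 0.5, 0.8.**
- Unstratified, both arms 0.515: 2.4%, 2.1%, 1.8%, 1.2%.
- Unstratified, both arms 0.30: 2.5%, 2.3%, 2.1%, 1.5%.
- Stratified: 2.4% to 2.7% throughout.

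The unstratified test is never inflated, and it becomes conservative as sites diverge.

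**Step 4: uneven accrual.** Two assumed sets of site totals were tried, each summing to 300 over three arms, with blocks of 6 (10,000 replicates, SE about 0.2 points). Set A: 75, 54, 42, 33, 24, 18, 15, 12, 9, 6, 6, 3, 3. Set B: 120, 72, 36, 18, 12, 9, 9, 6, 6, 3, 3, 3, 3. Over both comparisons:
- At SD 0, stratifying without pooling costs 1.0 to 1.5 points. Pooling sites with fewer than 12 randomised reduces that to 0.3 to 0.6.
- With pooling, the gain is +0.3 to +0.5 at SD 0.3, +1.2 to +2.1 at SD 0.5 and +3.5 to +4.9 at SD 0.8.

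**Step 5: a different convention.** If the hazard ratio of 0.514 is held within site instead of the whole-arm rates, the gain for AVATAR against drugs is +2.2 to +3.0 points at SD 0.5 and +8 to +9 at SD 0.75. The whole-arm proportions then no longer equal the SAP's, so the table above keeps to the SAP's figures. That is the more cautious choice, and its +5 is not a ceiling.

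**The case against.** The strongest case against is that this is an optional efficiency gain of unknown sign. The unstratified test is valid, the sample size was built on a log-rank test with no strata mentioned, and the primary comparison exceeds its planned power. At SD 0.3, already a wide spread of site rates, the gain is under half a point; at SD 0 it is a loss. The +5 needs drug-arm rates running from 31% to 94% across the middle 80% of sites. Making stratification primary also changes the meaning of the hazard ratio and needs a pooling threshold. All of this stands, and it sets the severity as low. It does not remove the mismatch between the randomisation and the analysis, for which the SAP gives no reason.

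Three stronger readings are tempting, and the documents support none of them.

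- *Leaving site out invalidates the test or leaves the trial short of power.* Null rejection stays at or below nominal in every setting, and at the SAP's whole-arm rates the primary comparison has more than 0.80 power at every SD tried.
- *It matters more for AVATAR against conventional ablation*, because Freedman power there is 0.787 and a conservative test would hide inferiority. The gains there are no larger at any SD above 0 (+0.2, +1.5, +4.9 against +0.4, +2.2, +5.0), and simulated unstratified power is 0.817 to 0.834. Local drug choice concerns an arm outside this comparison, and Protocol 6.1 and 6.3 have anti-arrhythmics stopped in both ablation arms after 4 weeks.
- *The optional clause lets the primary verdict be chosen after seeing results.* SAP 8.2 names the log-rank and proportional hazards analyses first and presents the covariate models as additional; the shells show the unadjusted analysis. The SAP does not offer a stratified log-rank test as an alternative, so disagreement between the two log-rank tests does not measure any such freedom. Even counting either log-rank test as a success, null rejection is only 2.7% to 2.9%.

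**Conclusion.** The point holds as a low-severity improvement. Site governs the randomisation but not the primary analysis, and site adjustment is left to unspecified extra models. The planned test is valid but conservative if sites differ: about 1.8% to 2.1% against a nominal 2.5% at SD 0.5.

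For AVATAR against drugs, stratifying changes power by about -1 point with no site differences, about 0 at SD 0.3, about +2 at SD 0.5 and about +5 only at the extreme SD of 0.8. AVATAR against conventional ablation is similar or slightly smaller. These figures rest on an assumed normal site effect, exponential times, no dropout, and whole-arm rates held at the SAP values. The direction of the net effect in this trial cannot be settled from the documents, because they give no between-site spread.

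**What to change.** In SAP 8.2, before data lock:

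1. Name the site-stratified log-rank test and the site-stratified Cox model as the primary analysis for both comparisons.
2. Fix a rule for pooling small sites. Fewer than 12 randomised is the illustration used here; the trial team should set its own threshold.
3. Report the unstratified log-rank and Cox results as a sensitivity analysis.
4. Label the hazard ratio as within-site.
5. State the strata in the shells for Tables 4.2 and 4.3.

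The cost is SAP wording and two shells, with no new data. If sites do not differ, the price is about 0.3 to 1.5 points of power (0.3 to 0.6 with pooling under uneven accrual). The hazard ratio also takes a within-site meaning: for the same whole-arm rates at SD 0, 0.5 and 0.8 it would be 0.51, 0.48 and 0.44 for AVATAR against drugs, and 0.44, 0.42 and 0.39 for conventional against AVATAR. The label is therefore needed.

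A lighter alternative is to declare the unadjusted analysis primary and pre-specify the stratified one as a sensitivity analysis. That would remove the ambiguity about site but would not recover the power.
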